13. STATISTICAL METHODS

A statistical analysis plan (SAP), providing details about the specific planned analyses and hypothesis tests, will be prepared and approved by the Sponsor and its designees prior to study database lock, propensity score determination, and unblinding of the double-blind subject treatment assignments.

13.1. Efficacy Analysis

13.1.1. Analysis Populations

The following subject populations will be evaluated and used for presentation and analysis of the data:

- The Randomized Population will include all randomized subjects.
- The Intent-to-Treat (ITT) Population will include all randomized subjects who receive any amount of investigational product (OCA or placebo). The ITT Population will be the primary population used for efficacy analyses. Treatment assignment will be based on the randomized treatment.
- The Safety Population will include all subjects who received any amount of investigational product (placebo or OCA). The Safety Population will be the primary population used for safety analyses. Treatment assignment will be based on the treatment actually received.
- The PK population will include all OCA subjects who have at least one confirmed fasted analyzable sample. Subjects must have been fasting for approximately 8 hours prior to the visit and must not have any major protocol deviations that potentially affect exposure levels. The PK population will be used for OCA PK analyses.
- The Overall Historical Control Population will include subjects from the United Kingdom (UK) -PBC Group and Global PBC Study Group databases with demonstrated comparability to randomized subjects in this clinical study (747-302) with respect to both subject characteristics and disease progression.
- The UK-PBC Historical Control Population will include subjects from the UK-PBC Group databases with demonstrated comparability to randomized subjects in this clinical study (747-302) with respect to both subject characteristics and disease progression.
- The Global PBC Historical Control Population will include subjects from the Global PBC Study Group database with demonstrated comparability to randomized subjects in this clinical study (747-302) with respect to both subject characteristics and disease progression.

13.1.1.1. Comparability of Historical Controls

Utilization of both historical control/observational databases (UK-PBC and Global PBC Study Group), with more than 6000 subjects each, allow for a rigorous subject level meta-analysis. The historical databases include long-term follow up, detailed subject-level information such as

baseline clinical characteristics, longitudinal liver biochemistry, and long-term outcomes, and span a broad range of subject characteristics that may influence disease (disease state, age, gender, and regional differences in standard of care). Historical controls from both databases will be chosen based on the same study inclusion/exclusion criteria where possible.

13.1.2. Determination of Sample Size

The following assumptions were used in sample size calculations:

- Exponential survival curves, placebo survival estimate of 0.5 at 8 years with a hazard ratio of 0.60, and total study duration of 8 years, allowing for 2 years accrual and 6 years of follow up.
- Subjects will be randomized in a 1:1 ratio to placebo or OCA.
- The 2 groups will be compared using a 2-sided log rank test at the 5% level of significance.

Based on the randomization ratio, significance level, and assumed hazard ratio, a total of 121 events (both groups combined) will provide 80% power to demonstrate a statistically significant difference between OCA and placebo on time to liver-related outcomes, including all-cause mortality.

In addition, based on the remaining assumptions stated above, it is estimated that approximately 350 subjects will be enrolled to attain 121 events.

13.1.2.1. Sample Size Re-Estimation Plan

Conducting a long-term outcomes study given the low disease prevalence, relatively slow disease progression, and ethical considerations, which in combination will impact recruitment and event rates, is inherently difficult. As stated in ICH E9, in long-term trials there is an opportunity to check the assumptions that underlay the original design and sample size calculations. The power stated above depends on the total number of events. Thus, the overall survival function can be estimated without unblinding.

Therefore, starting approximately 2 years after the first subject is randomized, the aggregate event rate and sample size based on recruitment and retention will be evaluated in a blinded manner quarterly. This evaluation will determine if any increases in number of subjects are required in order to obtain a total of 121 adjudicated events for the final analysis in the combined groups. Specifically, the pooled number of events will be available during the study in a blinded manner, without any knowledge of the comparative efficacy in the treatment groups. This method for evaluating the sample size does not inflate the type I error rate. Additional subjects may be enrolled as appropriate.

If after 4 years of accruing subjects, despite increases in the number of subjects, it is determined that at least an additional 2 years (ie, total study duration of at least 10 years) are needed to randomize sufficient subjects to achieve a total of 121 adjudicated events, all subjects enrolled from that point forward will receive open-label OCA. Previously randomized subjects will continue to be treated in a blinded manner with either OCA or matching placebo. If this modification is implemented, the alternative primary efficacy analysis is specified in [Section 13.1.9](#).

Any revised sample size or changes to treatment allocation will be justified and documented in a protocol amendment and in the CSR.

13.1.3. Primary Efficacy Analysis

The primary efficacy endpoint will be the time to first occurrence of one of the following post-randomization:

- Death (all-cause)
- Liver transplant
- MELD score ≥ 15
- Hospitalization (as defined by a stay of 24 hours or greater) for new onset or recurrence of:
 - Variceal bleed
 - Encephalopathy (as defined by a West Haven score of ≥ 2)
 - Spontaneous bacterial peritonitis (confirmed by diagnostic paracentesis)
- Uncontrolled ascites (diuretic resistant ascites requiring therapeutic paracentesis at a frequency of at least twice in a month).
- Hepatocellular carcinoma confirmed by 2 complimentary imaging modalities.

The primary efficacy analysis will compare randomized OCA to randomized placebo with respect to the primary efficacy endpoint using the ITT population. Only adjudicated events will be included in analyses. The 2 treatment groups will be compared using the log rank test stratified by the randomization stratification factor. Kaplan-Meier (KM) estimates of the distribution of the time-to-event will be tabulated and graphed by treatment group. The tabulation will include the KM estimate of the medians and corresponding 95% confidence intervals (CIs), if the medians can be estimated. The number and percent of subjects censored and with events will be presented. The hazard ratio and 95% CI will be determined based on a Cox regression model stratified by randomization strata to estimate the magnitude of the effect.

13.1.4. Key Secondary Efficacy Analyses

The key secondary efficacy endpoints will compare OCA to placebo on the following:

- Time to first occurrence of MELD score ≥ 15
- Time to liver transplant or death (all-cause)
- Change from Baseline in total bilirubin at end of study
- Change from Baseline in ALP at end of study

The key secondary efficacy analyses will compare randomized OCA to randomized placebo in ITT population with respect to the key secondary efficacy endpoints. Only adjudicated events will be included in time-to-event analyses. The comparison (hypothesis testing) will be conducted as specified in [Section 13.1.11](#) in a sequential closed testing gate-keeping procedure, provided that the primary efficacy endpoint comparison is statistically significant in favor of the

OCA treatment group. If the primary comparison is not statistically significant then comparison of the secondary endpoints will be considered as descriptive and exploratory. This procedure controls the study-wise type I error.

The 2 treatment groups will be compared using the same methodology as specified for the primary efficacy analysis ([Section 13.1.3](#)).

Analyses of change from Baseline to end of study in ALP and total bilirubin will be compared between treatment groups using analysis of covariance (ANCOVA) with change from Baseline as the dependent variable including treatment group and randomization stratification factor as fixed effects and the Baseline values as a covariate. The same analysis will be carried out using percentage change from Baseline as the dependent variable.

Descriptive statistics of the laboratory values will be summarized by treatment group. The results, change from Baseline, and percentage change from Baseline values as well as estimates of least-square means, standard errors, and 95% CIs will be presented by treatment group. Estimates of the mean difference between treatment groups, the standard error of the difference, and 95% CI of the difference will be presented.

13.1.5. Additional Secondary Efficacy Analyses

The following time to event secondary efficacy analyses will compare randomized OCA versus randomized placebo using the ITT population:

- Time to each component of the primary efficacy endpoint (except MELD score ≥ 15 which is captured above)
- Time to development of varix/varices
- Time to liver-related death
- Time to liver-related death or liver transplant
- Time to liver-related death, liver transplant, or MELD score ≥ 15

The same analysis methodology as used for the primary efficacy analysis will be used for these secondary efficacy analyses. Similar endpoints, where available, will be analyzed to compare OCA to historical controls as described below in [Section 13.1.8](#).

Analyses of changes in liver biochemistry (GGT, ALT, AST, conjugated bilirubin, albumin, and INR) will be summarized and analyzed using the same methodology as specified in [Section 13.1.4](#) for the key secondary analyses of change in ALP and total bilirubin.

Analyses of changes in MELD score, Child-Pugh score, Mayo Risk Score (MRS), IgM, CRP, TNF- α , FGF-19, CK-18, C4, and ELF score will be summarized and analyzed using the Wilcoxon Rank Sum Test to compare treatment groups. The median differences and 95% CI of the median differences between treatment groups will be constructed using Hodges-Lehmann estimate. If the median differences between treatments are not symmetrical around the median, the Sign Test may be used.

13.1.6. Exploratory Efficacy Analyses

13.1.6.1. Responder Analyses

The percentage of subjects with a decrease in ALP of $\geq 15\%$ and $\geq 40\%$ from Baseline will be summarized by treatment group. In addition, the percentage of subjects with ALP \leq ULN will be summarized by treatment group.

The percentage of subjects that meet the criteria of a responder based on each of the definitions below will be summarized by treatment group. The response classification at baseline will also be included in the summary:

- ALP $\leq 3x$ ULN and AST $\leq 2x$ ULN and total bilirubin \leq ULN (Corpechot 2008)
- ALP $\leq 1.5x$ ULN and AST $\leq 1.5x$ ULN and total bilirubin \leq ULN (Corpechot 2011)
- ALP $\leq 1.67x$ ULN and total bilirubin \leq ULN (Momah 2012)
- Normal bilirubin (values \leq ULN) and normal albumin (values \geq lower limit of normal) (Kuiper 2009)
- ALP $\leq 1.76 x$ ULN (Kumagi 2010)

Responder analyses will compare treatment groups using a Cochran–Mantel–Haenszel test stratified by the randomization stratification factor. Missing values will be considered as a non-responder.

13.1.7. Pharmacoeconomic and Health Outcomes Endpoints

Sufficient data will be collected on resource utilization and quality of life to undertake cost-effectiveness analyses that are relevant to the major countries taking part in this study. Resource utilization data on hospitalizations, healthcare provider visits, and medications will be combined with appropriate national unit costs to calculate a cost per patient per year in the study.

Quality of life data from patient-reported outcomes measures will be combined with survival data to calculate quality adjusted time in the study per patient. Cost-effectiveness analyses will report the incremental cost per major clinical outcome averted, liver-related death averted, life-year gained and quality-adjusted life year gained, including OCA as part of usual care versus usual care without OCA. Analyses will be conducted within the study and using a lifetime perspective. A separate economic analysis plan will be prepared and reported separately from this protocol.

13.1.8. Supportive Analysis

Per the International Conference on Harmonisation (ICH) E10 guidance, “where no obvious single optimal external control exists, it may be advisable to study multiple external controls”. In order to address the risks associated with the inclusion of a long-term placebo arm, supportive analyses of the primary endpoint will compare clinical outcomes in the OCA treatment arm to historical controls.

In an attempt to avoid the inherent biases with historical controls and to maintain the integrity of this comparison, one can invoke matching methods to optimize comparability and find a historical control that is “similar” to a participating subject. The historical database control

should be as similar as possible to the study population and should have been exposed to a similar standard of care (see [Section 5.5.2.2](#)).

A propensity score can be used to reduce bias through matching, stratification, regression adjustment, or some combination. Propensity scores use information from a pool of patients who do not participate in the study (historical controls) to identify what would have happened to participating subjects in the absence of the treatment. By comparing how outcomes differ for treated subjects relative to historical controls, it is possible to estimate the effects of the treatment.

Although it might be relatively simple to assign a historical control based on a single observable characteristic, in practice, if the matching process is to successfully mitigate potential bias, it has to be done considering a full range of covariates across which the treatment and historical controls might differ. Although the results of using matching controls are conditional only on the observed covariates, if one has the ability to measure many of the covariates that are believed to be related to the treatment assignment, then one can be fairly confident that approximately unbiased estimates for the treatment effect can be obtained. Both UK-PBC Group and the Global PBC Study Group formally collect numerous covariates that could be used for propensity score estimation including standard of care, eg, UDCA.

Historical controls will be chosen based on the same inclusion/exclusion criteria where possible.

Propensity scores will be estimated using the available covariates that predict receiving the treatment. Only covariates and not outcome variables will be included in the propensity score estimation. Therefore, there is no chance of biasing results in favor of one treatment.

The covariates and factors collected in the historical databases will be specified in the SAP.

Propensity scores will be estimated first through a logistic regression model with treatment group as the dependent variable and the above covariates/factors as independent variables. Then the stratum boundaries are determined based on the propensity score values for both groups (OCA population and control [historical and randomized placebo]) combined or in the OCA population or historical control group alone. Based on recommendations in the literature, quintiles of the estimated propensity score from the combined group will be used to determine the stratum boundary cut-offs for the different strata.

Outcome events collected in the historical database are: death (liver-related and all-cause), liver transplant, hepatocellular carcinoma, and other. Other is defined as cirrhosis or decompensation such as ascites, variceal bleed, and encephalopathy.

The propensity score quintile will be then be used as the stratification factor in the stratified log rank test to compare randomized OCA-treated subjects in the ITT population and historical controls (Overall Historical Control Population: both the UK-PBC Group and Global PBC Study Group databases) on the following outcomes:

- Time to death (all-cause)
- Time to liver-related death
- Time to liver transplant
- Time to liver transplant or death (all-cause)

- Time to liver transplant or liver-related death
- Time to hepatocellular carcinoma

KM estimates of the distribution of the time-to-event will be tabulated and graphed by treatment group. The tabulation will include the KM estimate of the medians and corresponding 95% CIs if the medians can be estimated. The number and percent of subjects censored and with events will be presented. The hazard ratio and 95% CI will be determined based on a Cox regression model stratified by randomization strata to estimate the magnitude of the effect.

Sensitivity analyses will be conducted limiting to the separate individual historical control databases, ie, UK-PBC Group and Global PBC Study Group. To evaluate the robustness of the propensity score estimations, additional algorithms and factors may be considered.

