13.1.2. Determination of Sample Size

The following assumptions were used in sample size calculations:

- Exponential survival curves, placebo survival estimate of 0.5 at 8 years with a hazard ratio of 0.60, and total study duration of 8 years, allowing for 2 years accrual and 6 years of follow up.
- Subjects will be randomized in a 1:1 ratio to placebo or OCA.
- The 2 groups will be compared using a 2-sided log rank test at the 5% level of significance.

Based on the randomization ratio, significance level, and assumed hazard ratio, a total of 121 events (both groups combined) will provide 80% power to demonstrate a statistically significant difference between OCA and placebo on time to liver-related outcomes, including all-cause mortality.

In addition, based on the remaining assumptions stated above, it is estimated that approximately 350 subjects will be enrolled to attain 121 events.

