13.1.8. Supportive Analysis

Per the International Conference on Harmonisation (ICH) E10 guidance, “where no obvious single optimal external control exists, it may be advisable to study multiple external controls”. In order to address the risks associated with the inclusion of a long-term placebo arm, supportive analyses of the primary endpoint will compare clinical outcomes in the OCA treatment arm to historical controls.

In an attempt to avoid the inherent biases with historical controls and to maintain the integrity of this comparison, one can invoke matching methods to optimize comparability and find a historical control that is “similar” to a participating subject. The historical database control

should be as similar as possible to the study population and should have been exposed to a similar standard of care (see [Section 5.5.2.3](#)).

A propensity score can be used to reduce bias through matching, stratification, regression adjustment, or some combination. Propensity scores use information from a pool of patients who do not participate in the study (historical controls) to identify what would have happened to participating subjects in the absence of the treatment. By comparing how outcomes differ for treated subjects relative to historical controls, it is possible to estimate the effects of the treatment.

Although it might be relatively simple to assign a historical control based on a single observable characteristic, in practice, if the matching process is to successfully mitigate potential bias, it has to be done considering a full range of covariates across which the treatment and historical controls might differ. Although the results of using matching controls are conditional only on the observed covariates, if one has the ability to measure many of the covariates that are believed to be related to the treatment assignment, then one can be fairly confident that approximately unbiased estimates for the treatment effect can be obtained. Both UK-PBC Group and the Global PBC Study Group formally collect numerous covariates that could be used for propensity score estimation including standard of care, eg, UDCA.

Historical controls will be chosen based on the same inclusion/exclusion criteria where possible.

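### In the registry comparisons the propensity score enters only the log-rank test; the survival curves, medians and event percentages are set by treatment group without adjustment and carry any remaining baseline imbalance

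*Protocol*

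**What the plan says.** The current text is Protocol Version 3; the preceding protocol version has the same wording in the same sections.

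- **Premise (13.1.8).** For matching to mitigate bias it must consider "a full range of covariates across which the treatment and historical controls might differ".
- **Test (13.1.8).** A logistic model gives a propensity score. Its quintile is the stratification factor of the log-rank test of randomized OCA against the pooled historical controls.
- **Display (13.1.8).** The next paragraph says "KM estimates of the distribution of the time-to-event will be tabulated and graphed by treatment group". Medians with 95% CIs, if estimable, and numbers and percentages of subjects with events and censored follow. No weighting, standardisation or within-quintile display is mentioned.
- **Hazard ratio (13.1.8).** The Cox model is stratified by randomization strata, so it does not use the propensity score either.
- **Alternative primary analysis (13.1.9).** The same test and the same display apply to all OCA subjects against randomized placebo plus historical controls, on time to transplant or all-cause death.
- **Selection of controls (13.1.1, 13.1.1.1, 13.1.8).** Trial eligibility criteria are applied to the registries as far as possible, and comparability must be demonstrated. No criterion for comparability is given.

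**The concern.** The display paragraph closely repeats the one in 13.1.3. There it describes randomized OCA against randomized placebo, and a by-group curve estimates what it should. In 13.1.8 and 13.1.9 the groups were not formed by randomization as a whole. A by-group curve then compares two populations whose baseline risk may differ, which is the problem the propensity score is brought in to handle.

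The curves, medians and event percentages are the only absolute-scale outputs that these sections specify. If 13.1.9 is triggered, they will illustrate the primary efficacy result. A reader could see separated curves beside a null stratified test, or overlapping curves beside a positive one, with no means of telling case mix from effect. Correcting the stratification of the Cox model would not change the curves.

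**Working it through.** **1. The plan's own figure.** Section 13.1.2 states "The 2 groups will be compared using a 2-sided log rank test at the 5% level of significance", "placebo survival estimate of 0.5 at 8 years with a hazard ratio of 0.60" and "a total of 121 events (both groups combined) will provide 80% power to demonstrate a statistically significant difference". Schoenfeld's formula with 1:1 allocation gives 4 × (1.960 + 0.842)² / (ln 0.60)² ≈ 120.3, hence 121 events (power 80.2%). The figure reproduces, but it sizes the randomized comparison on the composite endpoint. The protocol gives no effect size, event rate or sample size for the registry comparison, so no figure in it measures this point.

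**2. What by-group curves do, in a case that can be checked by hand.** Take five propensity strata and no treatment effect. The middle stratum has hazard ln 2 / 8 per year, and adjacent strata differ by an assumed factor of 1.25. Eight-year survival by stratum is 0.5 raised to 0.64, 0.8, 1, 1.25 and 1.5625, that is 0.642, 0.574, 0.500, 0.420 and 0.339. Assume a mild imbalance in stratum mix.

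- OCA (16/18/20/22/24%): 0.16×0.642 + 0.18×0.574 + 0.20×0.500 + 0.22×0.420 + 0.24×0.339 = 0.480
- Controls (24/22/20/18/16%): 0.24×0.642 + 0.22×0.574 + 0.20×0.500 + 0.18×0.420 + 0.16×0.339 = 0.510
- By-group difference: −3.0 points
- Control curve reweighted to the OCA mix: 0.480, difference 0

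With a factor of 1.5 the difference is −5.3 points. Reversing the risk gradient reverses the sign. With equal mixes it is zero.

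**3. Continuous-score illustration.** All inputs here are assumptions except the 0.5 survival level, which is borrowed from 13.1.2. There are 175 OCA subjects (half of 350) and 2000 controls, no treatment effect, one normal prognostic score z with SD 1, a mean difference of 0.2 to 0.6 SD, and censoring between 6 and 8 years. Survival in a group with score mean m is the average of exp(−λ t e^(βz)) over z ~ N(m, 1), with e^β the HR per SD. The by-group artefact is the difference of these averages at t = 6. The ranges come from 200 simulated replicates per setting; numerical integration of the formula agrees with them.

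| 8-year survival, trial-type patients | HR per SD | Spurious 6-year difference (absolute, points) |
|---|---|---|
| 0.5 | 1.5 | 2.1 to 7.9 |
| 0.5 | 2.0 | 3.8 to 12.4 |
| 0.75 | 1.5 to 2.0 | 1.4 to 9.0 |

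At 8-year survival 0.5, standardising the controls to the OCA quintile mix leaves 0 to about 1.5 points. The 0.75 row is included because transplant or death is rarer than the composite; that value is also an assumption.

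**The case against.** **Unadjusted is an inference.** The protocol never uses the word, weighted curves are also drawn by treatment group, and analysis detail is left to the SAP. This stands in part, and a SAP could supply adjusted curves. But the protocol names the step where the quintile is used and then fixes the display in the wording of the randomized analysis. A SAP that followed it literally would produce unadjusted curves.

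**Controls are selected to be comparable.** This stands as mitigation. It makes the upper end of the illustrated range hard to present as typical. It does not remove the risk, because eligibility is matched only as far as possible and comparability has no criterion.

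**The curves decide nothing.** Inference rests on the stratified test, and the hazard ratio is the designated measure of effect size. The 13.1.8 analysis is supportive, and 13.1.9 is contingent on a change to allocation that needs an amendment. This stands and limits the severity.

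**Medians may not be reached.** Even at the composite's planning rates the OCA median would be 8/0.60 = 13.3 years, against an 8-year study. This stands: an OCA-versus-control contrast of medians is unlikely to be available.

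**Stronger readings that the documents do not support.** A reader might set the artefact against the 13.7 points that HR 0.60 implies at 6 years (0.5^(6/8) = 0.595 against 0.595^0.6 = 0.732) and quote it as a share of the effect sought. Those inputs belong to the randomized composite and are not set for transplant or death, so no such share should be quoted. A reader might also infer a bias in favour of OCA, or a biased test. The direction is unknown, and the test is stratified by propensity quintile.

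**Conclusion.** The point holds as a defect of specification in an output that is descriptive but prominent. In 13.1.8 and 13.1.9 the propensity quintile reaches only the log-rank test, and the absolute-scale results are laid down without adjustment, against the protocol's own premise. Whatever imbalance remains after control selection appears in full in the curves and event percentages.

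The size cannot be known from the documents. The range of about 2 to 12 points (about 1 to 9 at the lower event rate) rests wholly on the assumed imbalance and prognostic strength, and the artefact vanishes if the stratum mixes agree. It should be corrected, because 13.1.9 could become the primary analysis and the remedy is cheap. It does not invalidate the stratified test and does not touch the randomized primary analysis.

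**What to change.** In 13.1.8 and 13.1.9, specify that Kaplan-Meier curves, medians (if estimable) and survival differences at fixed years are standardised to the OCA group's propensity-stratum mix. Each control is weighted by the ratio of the OCA share to the control share in its stratum, with bootstrap 95% CIs. Keep the by-group curves and event percentages as output labelled unadjusted and descriptive. Settle this before propensity scores are determined and treatment is unblinded, the deadline that section 13 sets for the SAP.

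The cost is one sentence in each of two sections and some programming, with no new data. Intervals will be slightly wider. Five strata leave a small residual imbalance, and confounding by unmeasured covariates remains.
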